Impact of Behavioral Treatment of Insomnia on Nighttime Urine Production

University of Pittsburgh STUDY19110063

NCT03883724

INTRODUCTION

Nocturnal polyuria (NP) has long been known to be a major contributor to nocturia in the elderly. NP has a strong bidirectional relation with poor sleep especially in the elderly; however, to the best of our knowledge, an intervention directed solely at sleep has never been tried for NP. Our previous studies have shown that improving sleep with BBTI improves nocturia. However, we do not know the mechanisms by which behavioral sleep treatments improve nocturia. The proposed study will be the first to directly examine two plausible mediators: first uninterrupted sleep period (FUSP) and NP. The knowledge gained from this study can help identify 1) impact of sleep intervention on nighttime urine production, and 2) mechanisms by which sleep intervention improves nocturia

STUDY OVERVIEW

This pilot study will provide critical preliminary data regarding the relation between sleep and nighttime urine production in seniors by: 1) examining the impact of behavioral sleep treatment (BBTI- brief behavioral treatment of insomnia) on nighttime urine production- NP and 2) exploring the potential mechanisms by which BBTI impacts nocturia. To address the proposed aims we will perform a randomized controlled pilot trial of 60 healthy community-dwelling men and women aged 65 and over with nocturia and NP. The participants will be randomized to receive the 4-week behavioral sleep intervention BBTI by a trained therapist or an information control intervention. The participants will undergo detailed sleep and bladder assessments pre- and post-intervention to assess the effect of treatment. Data from this study will provide feasibility and pilot data for a subsequent, larger, and more definitive trial.

Outcome measures:

- 1) Change in NP- measured by NPi- nocturnal polyuria index=(nocturnal urine volume/24-hour volume)*100
- 2) Change in nocturia frequency
- 3) Change in FUSP or duration of uninterrupted sleep before the first awakening to void

STUDY FLOW /STUDY PROTOCOL

Study Flow Chart					Post-intervention assessment		
Screening		Baseline assessment		Intervention			
		Visit 1	In-home Assessments	BBTI			
				Session			
Telephone Screening		Apnea Link Plus®	Detailed history & physical	Wk 1	Wk 1 Sleep/ Bladder diary Z-machine ISI		
				Tele call	Tele call		
		IC	Sleep/ Bladder diary Z-machine ISI	Wk 2	Wk 2 Tele call		

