				Wk 3	Wk 3 Tele call		
				Wk 4	Wk 4 Tele call		

Screening

Screening procedures include: a) telephone interview and b) Visit 1 to study research suite - Continence Research Unit at UPMC Montefore Hospital. If the subject is interested and qualifies, then the other visits are scheduled.

Telephone Interview

Use IRB approved telephone script to determine eligibility (5-20mins; study nurse/coordinator) ApneaLink mailed to participants who screened eligible upon telephone interview

Visit 1

2 hour; study nurse; in-person

1. Obtain informed consent and sign document.
2. Questionnaires:
 - Medical and Surgical history
 - Current medication
 - Current incontinence
 - ISI
 - MoCA (paper)
3. Uroflow and dip (at appropriate bladder fullness)
4. Measure flow rate and volume of normal void
5. Post-void residual measurement by ultrasound
6. Physical examination: Short physical examination.
7. Sleep/ bladder diary: Explain 3 day sleep and voiding diary instructions.
8. Zmachine: watch instruction video. The device to be worn on the 3rd night of voiding diary
9. Schedule visit 2 with enough time to complete diary.

Visit 2

Randomization

1. Follow study procedure according to the group randomized to.

Telephone follow-up

Week 2 after the visit 2- both groups (BBTI and Control)

Week 4 after the visit 2- both groups

Visit 3

For participants randomized to BBTI group

Post intervention

4 weeks post visit 2

1. Sleep/ Bladder diary (send in mail)
2. Zmachine (send in mail)
3. ISI- completed telephonically.

Inclusion/exclusion criteria

For this study researchers shall enroll: ambulatory and functionally-independent community-dwelling men and women aged 65+ years, with nocturia ≥ 2 /night.

Exclusion criteria:

- Unstable or acute medical or central nervous system conditions
- Untreated, current, severe psychiatric condition
- Untreated, current, severe overactive bladder syndrome
- Post void residual $> 30\text{ml}$
- Sleep apnea with $\text{AHI} \geq 15$
- Currently diagnosed and/or treated Obstructive Sleep Apnea, Restless Legs Syndrome, parasomnia
- CHF, by exam or NT-proB natriuretic peptide (NT-proBNP) $> 30 \text{ pmol/L}$
- Chronic kidney disease, stage III-V (eGFR < 60)
- > 14 alcohol drinks per week
- > 3 caffeinated drinks ($\sim 300\text{mg}$) per day

Statistical Analysis Plan

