Randomization: After all baseline assessments are complete, researchers will randomize the participants in to the intervention groups in a 1:1 ratio, with random block sizes chosen from small even numbers, stratified by severity of baseline nocturia (≤ 3 or > 3 /night). To prevent educated guessing, the study statistician will reveal exact details of blocking strategy only at study completion.

Data Analysis: In addition to statistical significance, researchers will employ descriptive statistics and graphical techniques to draw conclusions. Specifically, as appropriate for a pilot study, researchers will focus interpretations on magnitudes of effects from standard statistical methods rather than their p-values, and apply graphical techniques such as needle plots to represent data at the individual level rather than based on averages. Researchers will use SAS® version 9.3 (SAS Institute, Inc., Cary, North Carolina) software, intention-to-treat philosophy, and multiple imputation for missing data in all inferential analyses.

First, researchers will compare baseline characteristics between the group using independent samples t-, Wilcoxon rank sum, chi-square and Fisher's exact tests, as appropriate. Any significant differences will be used as additional covariates in sensitivity analyses. Second, researchers will fit a series of analysis of covariance (ANCOVA) models with pre- to post-intervention change in each outcome as the dependent variable, intervention group as the independent factor of interest, and baseline value of outcome as a covariate. Magnitude and significance of intervention group term will serve as evidence for Aim 1 efficacy hypotheses. Third, for Aim 2, researchers will begin by exploring correlations of pre- to post-intervention changes in nocturia with those in FUSP and NPI. In keeping with Baron and Kenny's framework for mediation analysis, researchers will add FUSP change and NPI change (both individually and together) as additional independent variables to the Aim 1 ANOVA models. Any subsequent reduction in intervention effect will be interpreted as supporting the Aim 2 mediation hypotheses. Statistical significance of the extent of mediation will be obtained using %SOBEL, %INDIRECT and %MEDIATE SAS® macros, as appropriate.

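### The Aim 2 rule counts a fall of any size in the intervention effect as support for mediation, and with no mediation such a fall occurs in about half of trials

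*Combined protocol and SAP*

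**What the plan says.** The Data Analysis part of the Statistical Analysis Plan first fits ANCOVA models for Aim 1: change in each outcome on group, adjusted for the baseline value. For Aim 2 it names the Baron and Kenny framework, and the researchers will "add FUSP change and NPI change (both individually and together) as additional independent variables". That gives three mediator models: FUSP alone, NPi alone, and both. The rule for reading them is: "Any subsequent reduction in intervention effect will be interpreted as supporting the Aim 2 mediation hypotheses". The next sentence reads: "Statistical significance of the extent of mediation will be obtained using %SOBEL, %INDIRECT and %MEDIATE SAS® macros, as appropriate". It gives no significance level or confidence level and does not tie the rule to the result.

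Earlier in the same part, the plan says that "researchers will focus interpretations on magnitudes of effects from standard statistical methods rather than their p-values". The Study Overview describes this aim as "exploring the potential mechanisms by which BBTI impacts nocturia", and the Introduction says the knowledge gained can help identify "mechanisms by which sleep intervention improves nocturia".

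**The concern.** A sign rule of this kind has no protection against chance. Adding a covariate that carries no mediation will still move the group coefficient up or down, and the rule counts every downward move as support. A reduction whose indirect effect is indistinguishable from zero would be reported as favouring the hypothesis, even though the planned macros will have supplied the figures that show this.

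At stake is the mechanistic reading of the pilot, which is meant to inform a larger trial. A label that chance alone produces about half the time is a poor basis for choosing which mechanism to pursue.

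**Working it through.** **Inputs from the documents.** 60 participants (Study Overview), randomised 1:1 (SAP, Randomization), so 30 per arm. Change in nocturia is regressed on group and baseline nocturia, then on one or both mediator changes (SAP, Data Analysis). The documents give no effect size, significance level or error rate for Aim 2, so there is no plan figure to reproduce. All path values below are assumptions, in SD units with unit-variance residuals.

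**Step 1: the identity.** Let a be the effect of group on a mediator, b the effect of that mediator on nocturia given group, c the group coefficient before adding mediators and c′ the coefficient after. In linear models on the same data with the same covariates:

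- one mediator: c − c′ = a×b (estimates)
- two mediators: c − c′ = a1×b1 + a2×b2

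If a or b is truly zero, the estimated product is roughly symmetric about zero. When c is clearly non-zero, the chance that |c′| < |c| is therefore about 1/2, largely whatever the sample size.

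**Step 2: how often the coefficient shrinks with no mediation.** The cases were a=b=0; a=0 with b=0.4; a=0.6 with b=0; and a mixed case (a1=0, b1=0.4, a2=0.6, b2=0). Direct effect was 0, 0.5 or 0.8 SD and mediator residual correlation 0, 0.3 or 0.6: 36 scenarios, 10,000 trials each.

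- Direct effect 0.5 to 0.8 SD: 0.49 to 0.52 in the two-mediator model and 0.48 to 0.52 in single-mediator models, outside the borrowed case in Step 5. In the borrowed case, runs gave 0.75 to 0.95.
- Direct effect possibly zero: 0.43 to 0.60 (two-mediator model). A second set of runs with a=0.8 or b=0.5, mediator correlation 0 or −0.5, and direct effects from 0 to 0.8 SD gave 0.37 to 0.61 per model.
- At least one of the three planned models: for two uncorrelated mediators, about 1 − 0.5×0.5 = 0.75. The second set gave 0.68 to 0.84.

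**Step 3: how large chance reductions are.** Among trials that show a reduction, with direct effect 0.5 to 0.8 SD, the 90th percentile in the two-mediator model was 0.08 to 0.32 SD. A hand check of the upper end: with a=0 the standard error of a is √(1/30 + 1/30) = 0.258. With b=0.4 for both mediators and correlation 0.6, the SD of the total reduction is about 0.258 × 0.4 × √(2 × 1.6) = 0.185, and 1.645 × 0.185 = 0.30, before allowing for error in b. A true indirect effect with a=0.6 and b=0.4 is 0.6 × 0.4 = 0.24 SD. Over all trials, not only those with a reduction, a two-mediator reduction above 0.24 SD occurred in about 0 to 11%.

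**Step 4: the same null cases read from an interval.** Percentile-bootstrap 95% CI (1,500 trials, 500 draws, resampled within arm; direct effect 0.5 SD, mediator correlation 0.3). The CI excluded zero in 0.2 to 4.6% per mediator in the two-mediator model, and in 0.2 to 5.0% in single-mediator models outside the borrowed case. A Sobel test at two-sided 0.05, in the second set of runs, gave at most about 2% per mediator.

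**Step 5: why neither model should decide alone.** Percentage of trials in which the CI excludes zero:

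| Situation | Single-mediator | Two-mediator |
|---|---|---|
| Borrowed: mediator moved by treatment, no effect on nocturia, correlated 0.3 with a prognostic mediator | 9% | 4% |
| Borrowed, correlation 0.6 | 27% | 3% |
| Upstream M1: treatment → M1 → M2 → nocturia (0.8, 0.6, 0.5; direct effect 0.3 SD) | 45% | 6% |
| True effect, a=0.6, b=0.4 | 55% | 51% |

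In the upstream case M1 carries a true effect of 0.8 × 0.6 × 0.5 = 0.24 SD, which the two-mediator model nearly always misses for M1. The total indirect effect from that model excluded zero in only 25% of those trials, so it is no substitute. An upstream arrangement is credible here, since the Introduction says "NP has a strong bidirectional relation with poor sleep especially in the elderly".

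**Step 6: what the interval cannot remove.** With a=0.6, b=0 and a mediator–outcome residual correlation of 0.2, 0.4 or 0.6 from shared recording error or an unmeasured common cause, the two-mediator CI excluded zero in 20%, 53% and 65% of trials (single-mediator: 22%, 55%, 65%). Sleep and voiding are recorded together (Visit 1: "Explain 3 day sleep and voiding diary instructions"), but a Zmachine is also worn on the third night and the documents do not say which instrument yields FUSP. This point is therefore conditional.

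**The case against.** The best defence is that the rule should not be read alone. The Data Analysis part names statistical significance among its bases for drawing conclusions, tests of the indirect effect come in the very next sentence, and treatment effects on NPi and FUSP are estimated under Aim 1. On that reading, support means one strand of evidence. This narrows the defect to an unstated link between two adjacent sentences, but that link is what decides whether a chance reduction counts, and the stated preference for magnitudes over p-values makes an implied significance condition less likely.

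The second defence is that reading magnitudes removes most of the problem. It has force: only about 0 to 11% of all null trials show a two-mediator reduction above 0.24 SD, and the 0.08 to 0.32 SD range applies only to trials that already show a reduction. The upper end arises when both mediators are prognostic. The range also refers to the total over two mediators, which matches the 0.24 SD benchmark only if one mediator is active. But the rule sets no magnitude, so this protection depends on the reader.

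Third, a CI criterion sits awkwardly with a plan that plays down p-values, and it can mislead too, as Steps 5 and 6 show. That stands, and it is why the remedy calls for the estimates to be shown, an inconclusive category and a stated limitation. Finally, Aim 2 is exploratory within a pilot. That limits the consequence but does not make the rule sound.

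**Conclusion.** The concern holds. As written, the rule treats a reduction of any size as support and does not depend on the planned tests. With no mediation and a clearly non-zero intervention effect, it is met in about half of trials per model, more often in the borrowed case, and in about three quarters across the three models when the mediators are uncorrelated. The one-half figure rests on symmetry and is not sensitive to the assumed paths while the intervention effect is clear; with a weak or zero effect it ranges from about 0.37 to 0.61. The sizes of chance reductions, the power and the interval error rates all rest on assumed path values. The statement should be corrected before analysis. Aim 1 is unaffected.

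**What to change.** Replace the sentence with wording such as:

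> Aim 2 will be interpreted from the estimated indirect effect (a×b) for each mediator and its percentile-bootstrap 95% confidence interval, using the macros already listed. A reduction in the intervention coefficient whose indirect-effect interval includes zero will be reported as inconclusive, neither as supporting mediation nor as evidence against it.

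Then add:

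- Indirect effects from the single-mediator and two-mediator models are reported side by side, with neither as the sole deciding model. Where they disagree for a mediator, both are reported, with a statement that the data do not separate a borrowed reduction from an upstream mediator.
- A limitation: unmeasured mediator–outcome confounding, or shared recording error to the extent that nocturia, NPi and FUSP come from the same diary, can create an apparent indirect effect that the interval does not remove.
- One line on how the bootstrap is combined with the planned multiple imputation, and confirmation that the listed macros give this interval (the documents do not say).

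No new data are needed. The price is fewer positive statements: at n=60, with a=0.6 and b=0.4, 45% (100 − 55) of true effects in single-mediator models and 49% (100 − 51) in the two-mediator model would be called inconclusive. There will also be no single verdict when the models disagree.

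### Aim 2 counts any shrinkage of the group effect as support for mediation, but mediators and outcome are changes over the same interval, so a reverse path or a shared cause meets the rule equally

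*Combined protocol and SAP*

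**What the plan says.** The Introduction names "two plausible mediators: first uninterrupted sleep period (FUSP) and NP" of the effect of BBTI on nocturia. The third outcome measure in the Study Overview is "Change in FUSP or duration of uninterrupted sleep before the first awakening to void".

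On timing, the Study Overview says: "The participants will undergo detailed sleep and bladder assessments pre- and post-intervention to assess the effect of treatment". The Visit 3 section gives one post-intervention point, "4 weeks post visit 2", with a combined sleep and bladder diary, the Zmachine and the ISI. The telephone contact at week 2 lists no measurement. The flow chart is broken in the available text and shows a diary beside a week 1 entry, but no interim value enters the analysis plan. The Visit 3 list stands under a line naming only the BBTI group. I take the measurements to apply to both arms, because the Study Overview and the ANCOVA require it.

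The Data Analysis section fits ANCOVA models of pre- to post-intervention change on group and baseline outcome. For Aim 2 it correlates nocturia change with FUSP change and NPi change, then adds those changes, singly and together, to the Aim 1 models. I read nocturia as the Aim 2 outcome. The rule follows: "Any subsequent reduction in intervention effect will be interpreted as supporting the Aim 2 mediation hypotheses". Significance of the extent of mediation comes from the %SOBEL, %INDIRECT and %MEDIATE macros. The section gives no reverse model, no caveat on direction and no allowance for common causes of mediator and outcome.

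**The concern.** Randomisation protects the comparison of arms on nocturia and on each mediator. It does not protect the link from mediator change to nocturia change, which is an observational association between two quantities recorded over the same interval.

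At least two other structures produce that association. First, nocturia may drive the mediator. FUSP ends at the first void of the night, so a participant with fewer voids will tend to have a later first void and a longer FUSP, whatever the cause of the fewer voids. Second, an unmeasured factor may move both. In either case, conditioning on the mediator takes away part of the group coefficient, and the rule counts this as support.

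What is at stake is the Aim 2 conclusion. The Introduction offers the mechanism of benefit as one of the two kinds of knowledge the study can yield, and the Study Overview says the data will serve a larger trial. A variable that merely follows from nocturia could be put forward as that mechanism.

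**Working it through.** **Inputs from the documents:** 60 participants, 1:1 allocation (30 per arm); change-score ANCOVA with baseline outcome; mediator change added as a regressor; the any-reduction rule; the Sobel test. The plan gives no effect size, SD, correlation or alpha for Aim 2, so there is no figure of its own to reproduce.

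**Assumptions:** unit within-arm SDs; treatment effect c of 0.5 or 0.8 SD on nocturia change; slope g of mediator change on nocturia change from 0.3 to 0.7; two-sided 0.05.

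**Step 1: pure reverse path, no mediation.** Let Y = cT + e and M = gY + √(1 − g²)·u, where e and u are independent with variance 1.
- Effect of group on M: a = gc.
- Within-arm variance of M: g² + (1 − g²) = 1. Within-arm covariance of M and Y: g. So the coefficient of M in the model for Y is b = g.
- Apparent indirect effect: ab = g²c. Group coefficient after adding M: c(1 − g²).

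The proportion removed is g²: 0.4² = 16%, 0.5² = 25%, 0.6² = 36%.

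**Step 2: forward twin.** Take a true partial mediator with M = gcT + u and Y = gM + c(1 − g²)T + √(1 − g²)·e. It has the same means and covariances as Step 1. Fitted to the same simulated data, the saturated forward and reverse models had equal log-likelihoods every time (largest difference about 5 × 10⁻¹⁴). No test that uses only these variables can therefore choose between them.

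**Step 3: shared cause.** If M and Y each receive effect c from treatment and share an unmeasured cause giving within-arm correlation ρ, with no path between them, then a = c and b = ρ. The proportion removed is ρ: 30% to 70% for ρ from 0.3 to 0.7.

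**Step 4: frequencies.** Simulation under Step 1, 30 per arm, about 4,000 trials per scenario. Frequencies vary by 1 to 2 percentage points between runs.

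| Slope g | Mean reduction | Effect shrinks, 0.5 SD | Effect shrinks, 0.8 SD | Sobel p<0.05, 0.5 SD | Sobel p<0.05, 0.8 SD |
|---|---|---|---|---|---|
| 0.3 | 9% | 72% | 82% | 1% | 3% |
| 0.4 | 16% | 78% | 89% | 5% | 10% |
| 0.5 | 25% | 84% | 94% | 11% | 24% |
| 0.6 | 36% | 87% | 97% | 17% | 40% |
| 0.7 | 49% | 93% | 99% | 24% | 55% |

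**Step 5: comparator.** With no association between mediator and nocturia, the group effect still shrinks in about 50% of trials. With a shared cause but no effect of group on the mediator, it shrinks in about 50% to 54%. So part of each shrinkage figure comes from having no threshold; the excess over about 50% comes from the reverse path.

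**The case against.** **Exploratory aim, soft wording.** The Study Overview describes Aim 2 as exploring potential mechanisms in a pilot, and the rule speaks of support, not proof. This stands: a reader might infer that the plan will declare FUSP or NPi a proven mediator, and the text does not say so. But a pattern that a model without mediation produces in most trials gives little support even in the weak sense.

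**Self-contradiction.** A reader might infer that the plan contradicts itself, because the Introduction says "NP has a strong bidirectional relation with poor sleep especially in the elderly" while Aim 2 fits one direction. The documents do not bear this out. That sentence pairs NP with poor sleep, not with nocturia. For NP and nocturia the Introduction states one direction only, NP contributing to nocturia, and it presents better sleep as what improves nocturia. The point rests on the shared interval, the unrandomised mediators and the definition of FUSP.

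**Attention to magnitude.** The plan stresses effect sizes over p-values, and a full mediator would remove about 100% of the effect against g² for a pure reverse path. A 9% reduction would be seen as small. This stands in part. However, the rule itself ignores size, every reverse pattern has a partial-mediation twin of the same size, and playing down p-values also weakens the Sobel test as a safeguard.

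**Generic limitation.** Any two-wave mediation analysis has this limit. That is true, and it argues for stating the limit, whereas the plan adopts a rule that overlooks it.

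**Conclusion.** The concern holds for Aim 2 only; the Aim 1 comparison of arms is not affected. The any-reduction rule cannot distinguish mediation from a reverse path or a shared cause, and the named macros test the size of an assumed path, not its direction. This follows from the design and the algebra and does not depend on the assumed numbers.

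The size does depend on them. For slopes 0.4 to 0.6 with no mediation, the mean reduction is 16% to 36%, and the rule is met in roughly 78% to 97% of trials across treatment effects of 0.5 to 0.8 SD, against about 50% by chance. The planned Sobel test is a much stronger filter, at about 5% to 40%. At slope 0.3 the problem is smaller (9% reduction, Sobel 1% to 3%). Nothing here shows that the reverse path is what happens, only that the plan could not tell.

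**What to change.** Replace the rule in the Data Analysis section with wording such as:

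> The indirect effect will be estimated with a confidence interval. An interval excluding zero will be reported as consistent with mediation, but because mediators and outcome are measured over the same interval and the mediator is not randomised, direction and absence of confounding are not established.

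With each single-mediator indirect effect, report how it changes over an assumed correlation ρ between the residuals of the mediator model and the outcome model. If r is the observed within-arm mediator-outcome correlation (given the covariates) and s_Y and s_M are the residual SDs of nocturia change and mediator change given group and covariates, the mediator coefficient becomes

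b(ρ) = (s_Y / s_M) · [r − ρ·√((1 − r²)/(1 − ρ²))],

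and the indirect effect is a·b(ρ). It reaches zero at ρ = r, so that point alone only restates the observed association; show the whole curve. Describe it as a check on unmeasured confounding, not on direction.

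I would not add an interim diary for this purpose. It would also record nocturia that may already have changed, so it would not by itself establish order, and it would burden participants.

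Cost: a few sentences in the plan, a little extra analysis of data already collected, and a slightly weaker Aim 2 claim.
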